#### **9.4 Visit 9 (final study visit)**

1. Same procedures listed in for visits 2-8
2. Blood sample collected at beginning of dialysis treatment via dialysis access and usual dialysis procedures (at UW only)
3. Administer Home BP Device Experience Questionnaire.
4. Optional: Place 44-hour ambulatory blood pressure cuff and train patient on use (study team will also coordinate with patient return of 44-hour ambulatory blood pressure monitor). Administer 44-Hour ABPM Experience Questionnaire.

## **10 ADVERSE EXPERIENCE REPORTING AND DOCUMENTATION**

### **10.1 Adverse Events**

An adverse event (AE) is any untoward medical occurrence during a clinical investigation and that does not necessarily have a causal relationship with the study intervention. An AE is therefore any unfavorable and unintended sign (including an abnormal laboratory finding), symptom or disease that may or may not be associated with the administration of a study intervention.

The study team will probe, via discussion with the subject and review of the medical record, for the occurrence of AEs during each subject visit and record the information in the site's source documents. Adverse events will be recorded in the patient CRF. Adverse events will be described by duration (start and stop dates and times), severity, outcome, treatment and relation to study intervention, or if unrelated, the cause.

#### **AE Severity**

AE severity will be classified as:

**Table 1. AE Severity Grading**

Severity (Toxicity Grade)	Description
Mild (1)	Transient or mild discomfort; no limitation in activity; no medical intervention or therapy required. The subject may be aware of the sign or symptom but tolerates it reasonably well.
Moderate (2)	Mild to moderate limitation in activity, no or minimal medical intervention/therapy required.
Severe (3)	Marked limitation in activity, medical intervention/therapy required, hospitalizations possible.
Life-threatening (4)	The subject is at risk of death due to the adverse experience as it occurred. This does not refer to an experience that hypothetically might have caused death if it were more severe.

**AE Relationship to Study Intervention**

The relationship of an AE to the study intervention should be assessed using the following the guidelines in Table 2.

**Table 2. AE Relationship to Study Intervention**

Relationship to Intervention	Comment
Definitely	Previously known effect of intervention; or an event that follows a reasonable temporal sequence from administration of the intervention; that follows a known or expected response pattern to the suspected intervention; and that is not explained by any other reasonable hypothesis.
Probably	An event that follows a reasonable temporal sequence from administration of the intervention; that follows a known or expected response pattern to the suspected intervention; and that is unlikely to be explained by the known characteristics of the subject's clinical state or by other interventions.
Possibly	An event that follows a reasonable temporal sequence from administration of the intervention; that follows a known or expected response pattern to that suspected intervention; but that could readily have been produced by a number of other factors.
Unrelated	An event that can be determined with certainty to have no relationship to the study intervention.

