## 2.1 Risk / Benefit Assessment

This trial proposes to target an out-of-dialysis-unit SBP <140 mmHg vs. dialysis-unit SBP <140 mmHg among maintenance HD patients by adjusted estimated dry weight and anti-hypertensive medications. The algorithm will adjust RAAS inhibitors, beta-blockers, calcium channel blockers and other anti-hypertensive medications. The doses that will be prescribed will be within the scope of FDA approved doses. Potential risks of the study medications include: hypotension and bradycardia and associated symptoms such as dizziness. Subjects will be monitored for these potential risks closely through direct contact with the study coordinators. There is also a small potential risk of loss of confidentiality.

Blood pressure is one of the most important risk factors for cardiovascular disease and death in the general population. HD patients are at greatly increased risk of cardiovascular disease and death. So optimizing BP control in HD patients could potential yield substantial benefit. The proposed study is a pilot clinical trial test to test the feasibility and safety of treating dialysis-unit versus out-of-dialysis-unit blood pressure in dialysis patients. This will be most useful to practicing physicians, patients and public health planners.

Since the value of the findings is potentially large, we believe the proposed study's benefits outweigh the risks.

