### **14.3 Analysis of Primary Endpoint**

We will quantify the screen: enroll ratio. We will quantify rates of retention and adherence in each arm of the study and report characteristics of those lost to follow-up.

We will quantify % of patients in the home BP arm who can successfully complete home BP training, % who can transmit every other week home BP readings in a timely manner to the study team via any method and % who successfully implement electronic transfer of data via Bluetooth/smartphone.

Adverse events will be tabulated by treatment group and will include the number of patients for whom the event occurred, the rate of occurrence, and the severity and relationship to study intervention.

We will determine frequency of excessively high or low blood pressures, frequency of intra-dialytic hypotension and symptoms related to these in all enrollees.

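### The adverse-event relatedness classes in Table 2 overlap and leave a gap: a known effect can be Definitely related with no timing test, and some events fit no class

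*Combined protocol and SAP*

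**What the plan says.** Section 10.1 has every adverse event described by its relation to the study intervention or, where unrelated, by its cause. The relation "should be assessed using the following the guidelines in Table 2", which has four classes.

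- **Definitely** begins "Previously known effect of intervention; or an event that follows a reasonable temporal sequence from administration of the intervention". It goes on to require a recognised response pattern, and ends "and that is not explained by any other reasonable hypothesis".
- **Probably** requires timing, a recognised pattern, and that the participant's condition or other treatments are an unlikely explanation.
- **Possibly** requires timing and a recognised pattern, "but that could readily have been produced by a number of other factors".
- **Unrelated** is "An event that can be determined with certainty to have no relationship to the study intervention".

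Section 2.1 states: "Potential risks of the study medications include: hypotension and bradycardia and associated symptoms such as dizziness". Section 14.3, under the primary endpoint analysis, tabulates adverse events by treatment group with the number of patients, "the rate of occurrence, and the severity and relationship to study intervention".

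**The concern.** A relatedness scale should place each event in one class only, and its highest class should be the hardest to reach. Table 2 does neither reliably. The alternative at the head of Definitely gives known effects a route to the top class that skips a test the two lower classes impose. The certainty standard for Unrelated, with no class between it and Possibly, leaves some events with nowhere to go.

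This touches the events the trial most expects to see. Hypotension and dizziness are named risks of the medications, and sections 5.1 and 8.2.3 also ask about dizziness as a symptom of hypotension around dialysis sessions. Two assessors following the table in good faith could code the same episode differently. Section 7.2 makes the trial unblinded, and under section 10.2.1 the site investigator and study clinicians review the adverse-event reports. Ambiguous classes therefore leave room for attribution to be influenced by knowledge of the arm.

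**Working it through.** No arithmetic applies. No figure in the plan depends on the relatedness wording, and the documents give no adverse-event rates from which to estimate how many events would move. The check is a reading of the four classes against one another.

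**Step 1. Two readings of Definitely.** The punctuation allows either of these:

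- Reading A: a known effect is sufficient alone, and all the conditions after the word 'or' belong to the second alternative. The wording favours this. The text after 'or' has the same three-part form as Probably and Possibly, and its conditions attach to the noun 'event'.
- Reading B: 'or' joins only the first two items (known effect, timing), and the conditions on pattern and other explanations govern both.

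**Step 2. What each class requires.**

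| Class | Timing | Known pattern | Other causes |
|---|---|---|---|
| Definitely, known effect, reading A | not required | not required | no condition |
| Definitely, known effect, reading B | not required | required | no other reasonable explanation |
| Probably | required | required | other explanation unlikely |
| Possibly | required | required | other causes readily available |
| Unrelated | not mentioned | not mentioned | certainty of no relationship |

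On both readings a known effect can reach the top class without the timing that the two lower classes demand. The readings differ only on pattern and competing causes.

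**Step 3. Test cases.** These are hypothetical events run through the table, not trial data. Cases 2 and 3 can arise because section 8.1 makes no change when SBP is 100 to 140 mmHg, so an event can occur with no recent adjustment to time it against.

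| Event | Reading A | Reading B |
|---|---|---|
| 1. Dizziness soon after an adjustment; dialysis could readily explain it | Definitely and Possibly | Possibly |
| 2. Dizziness with no plausible timing; no other explanation found | Definitely | Definitely |
| 3. Dizziness with no plausible timing; dialysis a reasonable explanation; a link cannot be excluded with certainty | Definitely | no class |
| 4. Event that is not a known effect; no plausible timing; cannot be excluded with certainty | no class | no class |
| 5. Event with plausible timing but no known pattern and not a known effect; cannot be excluded with certainty | no class | no class |

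Case 1 shows the overlap under reading A. Case 2 shows the missing timing test under both readings. Case 3 changes class with the reading. Cases 4 and 5 show the gap, which does not depend on the 'or' at all.

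**Step 4. Where the classification is used.** Section 14.3 shows relationship as one element of the adverse-event table. The same section counts extreme blood pressures, intra-dialytic hypotension and related symptoms in all enrollees without attribution. Section 8.2.3 takes intra-dialytic hypotension from the dialysis record as a percentage of sessions. Section 10.2.1 documents serious events whether or not related, and section 16.2 reports them to the IRB regardless of causality. No stopping rule, reporting trigger or endpoint definition in the documents turns on the relatedness class.

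**The case against.** The strongest reply is that the table works well enough in practice. The closing condition of Definitely, "and that is not explained by any other reasonable hypothesis", may govern the whole entry, so that an episode dialysis could explain would not qualify. Possibly is written for events with competing causes. A previously known effect may mean an effect the intervention actually produced, not any event of the same type, and section 2.1 speaks only of potential risks. The table is offered as guidelines, and clinicians review the reports weekly. This is a descriptive pilot of 50 participants, and over-attribution to the intervention errs on the cautious side.

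Much of this stands, and it limits what can be concluded. A reader might infer that dialysis-related hypotension and dizziness will be misclassified in the safety tables. The documents do not support that: it takes reading A as settled and ignores Possibly. A reader might also infer that related-event counts will be uninformative, or that the arms will differ. Neither follows. Section 4.1 gives both arms the same target and algorithm, and the same Table 2 applies to both, so the wording creates no difference between arms by itself. Unblinded attribution could create one, and some subjectivity would remain under better wording.

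The reply does not remove the defect. Reading B still drops the timing test for known effects. The narrow sense of a known effect makes the entry circular, because it assumes the attribution the table is meant to decide. Calling the table guidelines does not help when the protocol offers no other rule. The gap between Possibly and Unrelated is untouched by any of these arguments.

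**Conclusion.** The point holds as a defect of wording: the four classes are neither mutually exclusive nor exhaustive. That known effects escape the timing test holds on either reading of the 'or'. That a known effect alone suffices, and that Definitely overlaps with Possibly, rests on the literal reading, which is the more natural but not the only one. The missing class holds whichever reading is taken.

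The supported consequence is that hypotension, bradycardia and dizziness can be classified inconsistently or drawn toward Definitely, and that some events cannot be classified at all. It is confined to the relationship column of the adverse-event table by arm. Its size cannot be stated from the documents. For a descriptive pilot whose main safety counts are made without attribution, this is a minor point that is worth correcting because the correction is nearly free.

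**What to change.** In Table 2, delete the opening known-effect alternative from Definitely, up to and including 'or'. The class then requires timing, a known pattern and no other reasonable explanation, which makes it the strictest of the related classes on either reading.

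Then either add an Unlikely class or relax the certainty standard in Unrelated. If a class is added, word it to take events that lack plausible timing, or lack a known pattern, but cannot be excluded with certainty; cases 4 and 5 above show that both are needed. An instruction to assign the highest class whose conditions are met would give every event exactly one class, since an event meeting Definitely would normally also satisfy Probably.

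Section 14.3 needs little change, because counts and rates regardless of attribution are already planned. The cost is the edits to Table 2, a matching CRF code-list change, and fewer events labelled definitely related. No target, algorithm or sample size is affected.

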**10.2 Serious Adverse Experiences (SAE)**

An SAE is defined as any AE occurring at any dose that results in any of the following outcomes:

- death
- a life-threatening adverse experience
- inpatient hospitalization or prolongation of existing hospitalization
- a persistent or significant disability/incapacity

Other important medical events may also be considered an SAE when, based on appropriate medical judgment, they jeopardize the subject or require intervention to prevent one of the outcomes listed.

### **10.2.1 Serious Adverse Experience Reporting**

Study sites will document all SAEs that occur (whether or not related to study drug) per UCSF CHR and UW IRB Guidelines. The collection period for all SAEs will begin after informed consent is obtained and end after procedures for the final study visit have been completed.

In accordance with the standard operating procedures and policies of the local Institutional Review Board (IRB), the site investigator will report SAEs to the IRB.

We will collect data on potential adverse events from several sources and incorporate them into the adverse event database. These sources include:

- Reports from participants of any occurrences of concern to them, to be obtained from calls to toll-free or local study numbers provided in the Consent Form and included in all post-enrollment Contact Forms
- Laboratory database and reports of new hospitalizations

Adverse events data from the study-site specific call lines will be reviewed weekly, as will AE reports from all sources, by the site PI and site study clinician(s), any Serious Adverse Events that are identified will be reported promptly to the DSMB and IRB(s).

### **10.2.2 Post-study Adverse Event**

We will continue to collect information on Adverse Events for up to 4 weeks after the study follow up period ends for all participants unless they ask us to not collect follow-up data.

## **11 DISCONTINUATION AND REPLACEMENT OF SUBJECTS**

### **11.1 Early Discontinuation of Study Intervention**

A subject may be discontinued from study intervention at any time if the subject or the investigator (Sponsor) feels that it is not in the subject's best interest to continue. The following is a list of possible reasons for study treatment discontinuation:

- Subject withdrawal of consent
- Subject is not adherent with study procedures
- Adverse event that in the opinion of the investigator would be in the best interest of the subject to discontinue study treatment
- Protocol violation requiring discontinuation of study treatment

- Lost to follow-up

If a subject is withdrawn from treatment due to an adverse event, the subject will be followed and treated by the investigator until the abnormal parameter or symptom has resolved or stabilized.

All subjects are free to withdraw from participation at any time, for any reason, specified or unspecified, and without prejudice.

Reasonable attempts will be made by the investigator to provide a reason for subject withdrawals. The reason for the subject's withdrawal from the study will be specified in the subject's source documents. Subjects enrolled at least 1 month should be encouraged to come in for a final visit (and the procedures to be followed would include those for their next scheduled visit).

### **11.2 Replacement of Subjects**

Subjects who withdraw from the study prior to 1 months will be replaced.

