	
pressure
 
4. Patients in whom systolic blood pressure is not measurable (e.g. those with left ventricular assist devices)
 
5. Hypotension: average pre-dialysis systolic blood pressure <100 mmHg over last 2 weeks prior to screening while not taking any blood pressure medications
 
6. Life expectancy <4 months
 
7. Anticipated living donor kidney transplant within 4 months

INTERVENTION	
 
• Dry weight and anti-hypertensive medication adjustment to target home systolic blood pressure vs. in-center pre-dialysis systolic blood pressure <140 mmHg
 

DURATION OF SUBJECT PARTICIPATION AND DURATION OF STUDY	The total duration of the study is expected to be 24 months
PRIMARY ENDPOINT	
 
• Feasibility of intervention
 
• Adherence to intervention
 
• Safety
 
• Tolerability
 

SECONDARY ENDPOINTS	
 
• Of the home BP participants, we will determine the modality they choose to transmit their home BP readings
 
• Differences in blood pressures between treatment groups as assessed by blood pressure at dialysis and 44-hour intra-dialytic ambulatory blood pressure
 

STATISTICS Primary Analysis Plan	
 
• We will quantify the screen: enroll ratio
 
• We will report the proportion of participants in the home BP arm that complete the training, percent of home BP readings completed over the study period, and mean time from home BP measurement to transmission to the study team.
 
• We will quantify rates of completion and drop out in each treatment arm.
 
• We will report rates of hypotension and hypertension in each treatment arm.
 
• We will quantify rate of intra-dialytic hypotension and symptoms related to intra-dialytic hypotension in each treatment arm.
 

Rationale for Number of Subjects	This pilot study is designed to test study logistics and optimize study interventions within the confines of a pilot study budget, not to find statistically significant differences between the two arms.

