#### Adherence

- We will determine what proportion of participants in the home BP arm successfully complete home BP training, perform home BP readings every other week and transmit data in a timely manner to the study team via any method.
- We will determine the drop out and completion rate in each arm.

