#### **7.6 Temporary Discontinuation**

Temporary discontinuation will be allowed in the study protocol in the event of hospitalization, travel out of town or other unavoidable breaks. Participants will be re-evaluated at hospital discharge or return to regular maintenance dialysis unit and resume participation in the trial barring any clinical contraindications. This mimics how study intervention would be implemented in actual clinical practice.

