#### **7.7 Lost to Follow-Up**

A participant will be considered lost to follow-up if he or she fails to engage in participants contacts (either by phone or in the dialysis unit) of greater than 1 month and is unable to be contacted by the study site staff.

The following actions must be taken if a participant fails to engage in contacts with the study team :

- The site will attempt to contact the participant and counsel the participant on the importance of maintaining the assigned contact schedule and ascertain if the participant wishes to and/or should continue in the study.
- Before a participant is deemed lost to follow-up, the investigator or designee will make every effort to regain contact with the participant. These contact attempts should be documented in the participant's study file.
- Should the participant continue to be unreachable, he or she will be considered to have withdrawn from the study with a primary reason of lost to follow-up.

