## **14 STATISTICAL METHODS AND CONSIDERATIONS**

Prior to the analysis of the final study data, a detailed Statistical Analysis Plan (SAP) will be written describing all analyses that will be performed. The SAP will contain any modifications to the analysis plan described below.

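### Do the undated one-month replacement rule and the unstated count of home readings due call for a change to the plan?

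*Combined protocol and SAP*

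**What the plan says.** Replacement takes one sentence in section 11.2: "Subjects who withdraw from the study prior to 1 months will be replaced". Section 11.1, just before it, uses the same length of time for another purpose: "Subjects enrolled at least 1 month should be encouraged to come in for a final visit". Consent is at Visit 0 (section 9.1) and randomization at Visit 1 (section 9.2). Neither section 11.1 nor 11.2 says which of them starts the month.

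Section 7.7 defines loss to follow-up by silence, applying to anyone who "fails to engage in participants contacts (either by phone or in the dialysis unit) of greater than 1 month", provided that site staff cannot reach them. Someone who stays unreachable is then classed as withdrawn: "he or she will be considered to have withdrawn from the study with a primary reason of lost to follow-up". That withdrawal is not given a date.

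On outcomes, the adherence part of section 5.1 states: "We will determine the drop out and completion rate in each arm". The synopsis adds, for the home arm, the "percent of home BP readings completed over the study period". Section 7.6 permits breaks: "Temporary discontinuation will be allowed in the study protocol in the event of hospitalization, travel out of town or other unavoidable breaks".

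On analysis, section 14.1 includes everyone randomized. Section 14.5 sets a target of 50 (25 per arm) on budget grounds and disclaims any aim of showing a significant difference. Section 14 defers detail: "Prior to the analysis of the final study data, a detailed Statistical Analysis Plan (SAP) will be written".

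**The concern.** Drop-out and adherence are primary outcomes of this pilot, so rules that decide who is replaced and which readings count deserve attention.

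The first worry is timing. If a lost participant's withdrawal is dated when the loss is declared, it can never fall inside the first month, so no silent loss is replaced. If it is dated at last contact, someone who goes silent soon after baseline is replaced. Consent and randomization are also both possible starts for the month. Two sites could read section 11.2 differently, and they would do so during enrolment, before the SAP has to exist.

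The second worry is the readings denominator. Readings due after a participant stops, or during an allowed break, can be counted as missed or left out, and the reported percentage depends on which is done.

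**Working it through.** **Target size.** 25 + 25 = 50. No power formula lies behind it, so there is no calculation to reproduce and none to upset.

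**Timeline.** Take 1 month as 30 days and day 0 as the start of the month. Loss can be declared at the earliest on (day of last contact + 31). Last contact on day 0, 7, 14 or 28 gives declaration on day 31, 38, 45 or 59. Dated by declaration, none of the four is replaced; dated by last contact, all four are. Each reading is workable by itself, so this is an ambiguity and not a contradiction.

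**Effect on completion.** Assumptions per arm: 1 active early withdrawal, 2 early silent losses, 3 later drop-outs, and each replacement in the arm of the person replaced. All randomized stay in the denominator (section 14.1).
- By declaration: randomized 25 + 1 = 26; completers 25 − 2 − 3 = 20; 20/26 = 76.9%. Both arms: 52 randomized, 40 completers.
- By last contact: randomized 25 + 1 + 2 = 28; completers 25 − 3 = 22; 22/28 = 78.6%. Both arms: 56 randomized, 44 completers.

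Drop-outs number 6 per arm either way (6/26 = 23.1%, 6/28 = 21.4%). With no silent losses the two readings agree.

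**Consent or randomization.** The documents give no interval between Visits 0 and 1, so this cannot be sized. The consequence is of the same kind: it decides whether one more person is recruited, while anyone already randomized stays in the analysis.

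**Readings after stopping.** Visits 2 to 9 imply 8 fortnights, so 25 × 8 = 200 home-arm sessions. Assume that those who continue do 90% (7.2 of 8), and that k participants stop after 3 due sessions with 2 done.
- Sessions done: (25 − k) × 7.2 + 2k.
- Due until stopping: (25 − k) × 8 + 3k. Due over the full period: 200.

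| k | Done | Due until stopping | % until stopping | % of 200 |
|---|---|---|---|---|
| 0 | 180 | 200 | 90.0 | 90.0 |
| 1 | 174.8 | 195 | 89.6 | 87.4 |
| 3 | 164.4 | 185 | 88.9 | 82.2 |
| 5 | 154 | 175 | 88.0 | 77.0 |

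The gap runs from 0 to 11 points. The first percentage drifts below 90 because those who stop are assumed to do 2 of 3 sessions. If they too do 90% while active, it stays at 90.0%, and 2 to 5 people stopping after 2 to 4 sessions gives 86.4% down to 76.5% of 200.

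**Readings in breaks.** If b of the 200 fortnights fall in allowed breaks and 90% of the rest are done, the result is 90.0% with breaks left out, against 0.9 × (200 − b)/200 with breaks counted: 87.8% for b = 5 and 85.5% for b = 10. The differences are 2.3 (2.25 unrounded) and 4.5 points.

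**The case for a change.** The best case for a change is that replacement is decided while recruitment is open, so a later SAP cannot settle it, and the budget is fixed. In addition, section 11.1 lists non-adherence as a reason to discontinue. If readings due after stopping leave the denominator, taking out non-adherent people raises reported adherence, and 11 points is not trivial in a study whose purpose is to measure adherence.

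Part of this stands. The sites could differ over replacing early silent losses, and the recruitment load would differ with them. That does not bias the arms: allocation is stratified by site (section 7.1), and replaced participants remain counted as drop-outs.

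The denominator point also stands as a matter of definition, but the text already leans one way. The synopsis wording and the all-randomized rule in section 14.1 point to the full period for people who stop, which leaves allowed breaks as the truly open case. There either convention is reasonable. The same question touches the participant-level measure in section 14.3, since someone who misses a fortnight in a permitted break may or may not count as transmitting every other week. Counting post-withdrawal readings as missed is itself a preference: it mixes retention into adherence when drop-out is already reported separately.

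**Conclusion.** The gaps are there, but the plan as written still gives sound results. Dating a loss when it is declared is a coherent reading of sections 7.7 and 11.2. The enrolment wording in section 11.1 goes part of the way to a start date. Whichever reading is used, the analysis set is unchanged; in the example, completion moves by 1.6 points and recruitment by 4 people.

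The readings percentage is more sensitive, at 0 to 11 points for stopping and 2.3 or 4.5 points for breaks. It is descriptive, it appears beside drop-out by arm, and no decision rule uses it. Defining which readings are due is ordinary SAP work that can be done before final analysis without affecting conduct. All sizes rest on assumed losses, stopping patterns and a 90% completion rate, since the documents give none. With no silent losses, no one stopping and no breaks, the differences shown here vanish. This is detail that the investigators and analysts can be expected to fill sensibly, and it does not call for a change to the plan.
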